## 1. Introduction and Study Overview

This Statistical Analysis Plan (SAP) describes in detail the planned analytical approaches for the above-mentioned randomized controlled trial. The study's objective is to evaluate the efficacy of a 6-month intervention combining Motivational Interviewing (MI) and a home-based rehabilitation program versus standard care in improving post-stroke outcomes. A total of 92 stroke patients were randomized (1:1) to the intervention or control group. Outcomes are measured at baseline, 1 month, 3 months, and 6 months post-intervention. The primary outcomes include depression (PHQ-9 score), fatigue (FSS score), cognitive function (MMSE score), and physical function (Barthel Index). Secondary outcomes include quality of life (Stroke Impact Scale) and exploratory fNIRS-based biomarkers of cortical activity. No interim analyses were conducted; all analyses described here are post-finalization of data collection. This SAP is finalized prior to unlocking the database to avoid data-driven decisions.

## 2. Analysis Populations

**Intent-to-Treat (ITT) Population:** The ITT population consists of all participants who were randomized, regardless of whether they completed the intervention or follow-up assessments. Each participant will be analyzed in the group to which they were originally assigned. The ITT population is the primary analysis set for efficacy outcomes, preserving the benefits of randomization.

**Per-Protocol (PP) Population:** The PP population is a subset of ITT including only those participants who completed the study with no major protocol deviations. For the intervention group, “completed the study” is defined as attending the majority of intervention sessions (at least 6 out of 8 MI sessions and at least 5 out of 6 months of rehab visits) and completing the 6-month follow-up assessment. For the control group, it entails completing the 6-month assessment and not adopting outside interventions similar to the study intervention. Major protocol deviations (if any occur, such as ineligibility discovered after randomization or failure to follow key procedures) will be listed and those cases may be excluded from PP analysis. The PP analysis will serve as a sensitivity analysis to see if results are consistent with the ITT analysis.

**Safety Population:** As this study involves minimal-risk behavioral interventions, no separate safety analysis population is defined; any adverse events will be descriptively reported for all enrolled participants.

### 3. Outcomes and Endpoint Definitions

#### Primary Efficacy Outcomes:

- **Depression Severity:** Change in Patient Health Questionnaire-9 (PHQ-9) score from baseline to follow-ups. The PHQ-9 is a 9-item scale (0–27 range); higher scores indicate worse depressive symptoms. The primary comparison will be the difference in mean PHQ-9 change from baseline to 6 months between groups. Additionally, trajectories over all time points will be considered. We will also examine the proportion of participants in each group achieving remission of depression (PHQ-9 < 5, for example) at 6 months as a supportive outcome.

- **Fatigue Level:** Change in Fatigue Severity Scale (FSS) score (range 9–63, higher = more fatigue). Same approach as PHQ-9: continuous score change and possibly categorization (e.g., FSS  $\geq 36$  indicating significant fatigue) for supplementary analysis.

- **Cognitive Function:** Change in Mini-Mental State Examination (MMSE) score (0–30, higher = better cognitive function). We will consider the mean change and group differences; additionally, the proportion of participants with cognitive impairment (MMSE  $\leq 24$ ) at each time point will be noted.

- **Physical Functional Independence:** Change in Barthel Index (BI) score (0–100, higher = more independent). Primary focus on mean score change at 6 months. Also, we may categorize outcomes (e.g., BI  $\geq 90$  as independent vs <90) for descriptive comparison.

Each of these primary outcomes will be analyzed as a continuous variable using appropriate parametric or nonparametric methods as outlined in Section 4. The primary time horizon for efficacy is the 6-month post-intervention assessment, though intermediate time points will be analyzed to observe trends.

#### Secondary Outcomes:

- **Quality of Life:** Stroke Impact Scale (SIS) 3.0 overall score (0–100, higher = better). Change in SIS from baseline to 6 months will be compared between groups. SIS subdomains (physical, emotion, communication, etc.) might also be explored for additional insights, but the overall score is the main focus.

- **Functional Near-Infrared Spectroscopy (fNIRS) Biomarkers:** Several exploratory endpoints derive from fNIRS measurements of cortical hemodynamics during a cognitive task:

- Mean or peak change in oxyhemoglobin ( $\Delta\text{HbO}_2$ , measured in  $\text{mmol}\cdot\text{mm}$  or arbitrary units) in predefined regions of interest (e.g., left orbitofrontal cortex, right orbitofrontal cortex, dorsolateral prefrontal cortex) at baseline, 3 months, and 6 months.
- The change in  $\Delta\text{HbO}_2$  from baseline to 6 months for those regions.

- We will specifically evaluate if the intervention group shows a greater increase in  $\Delta\text{HbO}_2$  in the left orbitofrontal cortex over time compared to controls, as prior evidence suggested a link between orbitofrontal activation and depression improvement.

- **Derived binary outcomes for ROC analysis:** e.g., “6-month depression status” (yes/no based on PHQ-9 threshold as noted) and using fNIRS metrics (such as 6-month  $\Delta\text{HbO}_2$ ) as predictors.

- **Other Clinical Measures:** If collected, the Modified Rankin Scale (mRS) for disability and NIH Stroke Scale (NIHSS) at baseline will be described but not tested as outcomes. The trial registration did not include these as outcomes, but baseline differences will be accounted for if necessary.

**Safety Outcomes:** The study will note any adverse events (AEs) or serious adverse events (SAEs) reported during the 6-month period, such as falls, medical complications, or psychological distress. Given the nature of the intervention, we do not anticipate intervention-related SAEs. AEs will be coded and summarized by group (e.g., number of falls during follow-up, any hospitalizations, etc.). No formal hypothesis testing on safety outcomes is planned due to expected low incidence and lack of power for such events.

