- **Home-Based Rehabilitation Program:** In addition to MI, intervention group patients engage in a personalized home exercise program guided by rehabilitation therapists. A physical therapist provides an initial assessment of each patient's functional abilities and limitations (covering mobility, basic activities of daily living, etc.) and, together with a multidisciplinary team (including occupational and speech therapists as needed), develops an individualized exercise plan. Therapy guidance is delivered through scheduled home visits and coaching sessions over the 6-month intervention period. Specifically, a therapist conducts home visits once a week during months 1–2, every 2 weeks during months 3–4, and once every 4 weeks during months 5–6. This tapering schedule provides more intensive support early on and encourages growing independence later. In total, participants receive approximately 12 home visit sessions (weekly for 8 weeks, biweekly for 8 weeks, monthly for 8 weeks). During each visit (~1 hour), the therapist trains the patient (and caregiver) in exercises and activities aimed at improving strength, balance, mobility, and self-care skills. Standard rehabilitation techniques are employed (passive/active range-of-motion exercises, strength training, task-oriented practice for daily activities, etc.), often using an audiovisual instructional DVD to standardize exercise routines. Example activities include gait training with a cane or wheelchair, practicing transfers and stair climbing, and fine motor tasks like using a key or preparing a drink. Caregivers are instructed on

how to assist and encourage the patient's independent function as much as possible. Patients keep a daily exercise log or diary to record their at-home practice outside of the supervised visits. The therapist's contact information is provided so patients/caregivers can consult with questions between visits. Any issues encountered at home are addressed through counseling or adaptation of the exercises (including additional education for caregivers on managing common problems). This home-based rehabilitation component is designed to complement the MI sessions by improving physical capabilities and thereby enabling patients to pursue the goals they set during MI.

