- **Intervention Period (Month 0 to Month 6):** The intervention group undergoes the structured program as described: MI sessions weekly in Month 1 and biweekly in Months 2–3 (8 sessions total), and physical therapist home visits weekly in Months 1–2, biweekly in Months 3–4, and monthly in Months 5–6. All intervention activities are logged. The control group receives no intervention during this period beyond usual care, though both groups continue to attend routine medical appointments as scheduled.
- **1-Month Follow-up (Month 1):** Both groups return for a follow-up visit at ~1 month post-baseline. Outcome assessments at this visit include PHQ-9, FSS, MMSE, Barthel Index, and SIS. These are administered by the study assessor to track early changes. (No fNIRS measurement is performed at 1 month in this study design.) The intervention group will have completed roughly four MI sessions by this point (if on schedule) and continues with weekly rehab visits through Month 2. The control group's visit consists of their routine check-up and outcome questionnaires.
- **3-Month Follow-up (Month 3):** A mid-point evaluation is conducted at 3 months for all participants. Outcome measures (PHQ-9, FSS, MMSE, Barthel, SIS) are administered again, and the **second fNIRS** assessment is performed for both groups under the same protocol as baseline. By Month 3, participants in the intervention arm will have completed the course of eight MI sessions (the final MI sessions occur around

week 10–12). They will also have had biweekly rehab visits through Month 3. The 3-month follow-up allows assessment of mid-intervention improvements and provides data for any necessary intervention adjustments. Control group participants continue to receive standard care and are assessed in parallel.

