All study data were collected in case report forms (CRFs) by the research staff at each visit. Baseline CRFs captured demographics and clinical history, while follow-up CRFs captured outcome assessments and any adverse events or additional treatments. Each participant was assigned a unique study ID; all data and samples (if any) were labeled with this ID to maintain confidentiality. The completed CRFs were double-checked by the study coordinator for completeness and accuracy after each visit. Data from CRFs were entered into a secure electronic database (password-protected) by two independent data entry personnel, with a third person performing comparisons to resolve any discrepancies (double data entry verification). The electronic dataset did not contain personal identifiers; a master link file connecting IDs to patient names was kept separately by the PI in a locked file.

Participants’ intervention adherence was monitored through session attendance logs, therapist records, and patient diaries (for home exercises). MI session attendance and quality were further monitored via the audio-recordings and supervision described earlier. Physical therapy home visit reports were reviewed weekly by the principal investigator to ensure the rehabilitation content was delivered as per protocol and to note any significant issues or deviations. Any protocol deviations or unexpected events were documented and discussed in weekly research team meetings.

Data quality control included range checks for data values (e.g., valid score ranges for questionnaires), and periodic audits of the consent forms and source data against the database entries. All original consent forms and paper records are stored in a locked cabinet in the Institute for Preventive Medicine and Public Health at Hanoi Medical University. Only the PI and authorized study team members have access to the keys and database password. We ensured compliance with Good Clinical Practice (GCP) guidelines in handling the data.

After study completion, the database will be locked and exported for analysis. The final de-identified dataset will be archived at Hanoi Medical University for a minimum of 5 years. Any blood samples or imaging data (if applicable, e.g. raw fNIRS recordings) will be stored without identifiers and used only for the purposes outlined in the study (with any future use requiring new ethical approval).

Ethics and Dissemination

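### The by-group adverse event table is open to unequal ascertainment, because the SAP does not restrict the source of events and one arm has about 23 to 25 study contacts against 3

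*SAP*

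**What the plan says.** **What is tabulated.** The Safety Outcomes paragraph of SAP section 3 takes any adverse or serious adverse event reported over the six months, and then: "AEs will be coded and summarized by group (e.g., number of falls during follow-up, any hospitalizations, etc". SAP section 5 plans one table of counts by group. Sections 2 and 3 make this descriptive, with no hypothesis test.

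**Where events are recorded.** The Protocol, under Data Collection, Management, and Quality Control, says "follow-up CRFs captured outcome assessments and any adverse events or additional treatments". Both arms attend at months 1, 3 and 6. The same section says "Physical therapy home visit reports were reviewed weekly by the principal investigator", and that unexpected events were documented and taken to weekly team meetings.

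**Contacts in the intervention arm only.** The Schedule of Events gives "MI sessions weekly in Month 1 and biweekly in Months 2–3 (8 sessions total"). The Home-Based Rehabilitation Program has the therapist visiting "once a week during months 1–2, every 2 weeks during months 3–4, and once every 4 weeks during months 5–6". Patients also keep a daily exercise diary, and "The therapist's contact information is provided so patients/caregivers can consult with questions between visits". Problems between visits have their own route: "Any issues encountered at home are addressed through counseling or adaptation of the exercises".

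**Control arm.** Controls have the same clinic check-ups and no therapist contact (Protocol, Control Group: Standard Care; Randomization, Allocation Concealment, and Blinding).

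Neither document says whether an event first noted at a home visit, at an MI session or in a diary enters the table, or whether a standard question elicits adverse events at the common visits.

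**The concern.** A count of reported events depends on how often someone was in a position to hear of them. Here that opportunity differs by arm by design, and the SAP's wording admits every source. A minor fall in an intervention patient may reach a therapist within a week or two. A control patient who falls just after month 3 has no study visit for about three months.

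The table is the only between-arm safety summary planned for a programme that includes gait, transfer and stair practice at home. If the intervention arm shows more falls, a reader cannot tell more falling from more asking. If the arms look alike, unequal capture could be hiding a lower true rate in the intervention arm.

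Raw counts add a second difficulty. One patient who falls repeatedly can dominate, and counts ignore unequal follow-up, although SAP section 4.3 expects dropouts.

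**Working it through.** **1. Home visits, against the Protocol's own total.** The Protocol states: "In total, participants receive approximately 12 home visit sessions (weekly for 8 weeks, biweekly for 8 weeks, monthly for 8 weeks"). Its schedule gives 8/1 + 8/2 + 8/4 = 8 + 4 + 2 = 14. The stated total of about 12 is not reproduced; 8 + 4 = 12 leaves out the two visits of months 5–6. Both figures are carried forward.

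**2. MI sessions.** Four weekly in month 1 plus four biweekly over the 8 weeks of months 2–3 = 8, as stated.

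**3. Post-baseline contacts.**
- Intervention, 14 home visits: 8 + 14 + 3 = 25.
- Intervention, 12 home visits: 8 + 12 + 3 = 23.
- Control: 3.
- Follow-up CRF only: 3 against 3.

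**4. Wait from an event to the next contact.** Assume a 24-week programme, follow-up visits at weeks 4, 12 and 24, and each home visit or MI session at the end of its interval. Contacts in the same week count once. For events spread evenly over time, mean wait = Σ(gap²) / (2 × 24).
- Control, gaps 4, 8, 12: (16 + 64 + 144)/48 = 4.7 weeks.
- Intervention, 14 home visits (eight gaps of 1, four of 2, two of 4; 14 contact weeks): (8 + 16 + 32)/48 = 1.2 weeks.
- Intervention, 12 home visits (the last two gaps merge into one of 8): (8 + 16 + 64)/48 = 1.8 weeks.

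**5. Illustration of size.** Assume equal true event rates, every contact feeding the tally, and a probability of 0.5^(wait/h) that an event is still reported at the next contact. The half-life h is not in the documents.

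| h (weeks) | Captured, control | Captured, intervention (14 visits) | Apparent ratio | Ratio with 12 visits |
|---|---|---|---|---|
| 4 | 0.511 | 0.828 | 1.62 | 1.50 |
| 8 | 0.692 | 0.907 | 1.31 | 1.25 |
| 13 | 0.791 | 0.941 | 1.19 | 1.15 |
| 26 | 0.886 | 0.970 | 1.09 | 1.08 |
| 52 | 0.941 | 0.985 | 1.05 | 1.04 |

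Under the same model with the CRF as sole source, the ratio is 1.0. The illustration supports a direction if the extra routes are used. It does not supply an estimate.

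**The case against.** The strongest reply is that the documents name one instrument for adverse events, the follow-up CRF, and both arms complete it on the same schedule. Read that way, there is no asymmetry in the schedule. A reader might infer from the contact counts that the comparison is biased. The documents do not support that, because they never say that events from home visits, MI sessions or diaries are added to the tally. No adverse-event role is given to the MI facilitators at all. Equally, the SAP does not confine the table to the CRF, so the risk stands even though the bias is not shown.

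A reader might also infer that exercise-related harms vanish because they are handled only by adapting the exercises. That does not follow either. Intervention patients complete the same CRF, and the Protocol says unexpected events were documented and discussed weekly.

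The table is descriptive, and events are expected to be few. With an assumed 10 events per arm, the 95% interval around a true rate ratio of 1 is exp(±1.96 × √(1/10 + 1/10)), about 0.4 to 2.4, which covers every ratio in the illustration. This limits what the table can show with or without the problem. It does not justify adding a systematic difference to the noise.

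On recall, the SAP tracks MMSE of 24 or below, but eligibility requires adequate cognition and excludes dementia. Poor recall is therefore plausible for some patients and not established. Hospital admissions are probably less exposed than falls; that is a judgement.

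Finally, the Protocol describes the trial as run in 2021–2022, and the SAP places all analyses after data collection. Changes to how events are elicited may come too late. That part of the objection stands and limits the remedy.

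**Conclusion.** The by-group table is open to differential ascertainment. The contact imbalance is certain (25 against 3, or 23 against 3 on the stated visit total). Whether it reaches the table is not settled by the documents. If it does, events would tend to be over-counted in the intervention arm by an unknown amount; 1.04 to 1.62 is the range under assumed half-lives of 4 to 52 weeks. If only the follow-up CRF is used, the scheduled opportunity is equal. Some imbalance could remain even then, because diaries and recent therapist visits may prompt recall and the assessor is not blinded.

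No efficacy estimate, test or error rate is touched. The matter is still worth settling in the SAP, because a better tabulation is available from records the trial already describes.

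**What to change.** In SAP sections 3 and 5:

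- Base the between-arm adverse event table on events recorded on the month 1, 3 and 6 follow-up CRFs in both arms.
- List events known only from home visits, MI sessions, diaries or team-meeting records separately, by source, as intervention-arm data outside the comparison. If a team-meeting record concerns a control patient, list it the same way under its own arm.
- Beside the counts, report patients with at least one event and events per person-month with 95% CI. The interval should allow for repeat events in one patient, for example by resampling patients.
- State the unequal contact between arms as a limitation.
- If any visits remain, ask the same adverse event question in both arms at the common visits. If data collection is complete, this item falls away.

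In the Protocol, reconcile the stated total of about 12 home visits with the 14 that its schedule implies.

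The cost is SAP wording and minor tabulation, and the efficacy analyses do not change. The downside is that the main comparison omits some events known only from intervention contacts, although they still appear in the separate listing.

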## 4. Statistical Methods

### 4.1 General Analysis Principles

All statistical tests will be two-sided with a significance level of  $\alpha = 0.05$ . Outcomes will be analyzed primarily in the ITT population. We will use **descriptive statistics** to summarize baseline characteristics and outcomes at each time point by group. For continuous variables, we will report means and standard deviations (or medians and interquartile ranges if non-normal). Categorical variables will be summarized as counts and percentages. No formal hypothesis testing will be performed on baseline characteristics (any baseline differences observed will be noted but understood as chance differences due to randomization). Where relevant, 95% confidence intervals (CIs) will be provided for estimated effects (e.g., mean differences, odds ratios). All analyses will be conducted using Stata (v16.0) and R statistical software. fNIRS signal processing will utilize MATLAB with the NIRSIT toolbox, with processed outputs then analyzed in Stata/R.

### 4.2 Baseline Comparisons and Participant Flow

We will construct a CONSORT flow diagram to document participant flow (screened, randomized, completed, lost to follow-up) by group. Baseline demographic and clinical variables (age, sex, stroke type, time since stroke, baseline PHQ-9, etc.) will be presented by group to check for any notable imbalances. Although randomization should create comparable groups, if any substantial differences are apparent (e.g., a significant age difference or stroke severity difference between groups), these variables may be considered for inclusion as covariates in sensitivity analyses of outcomes. Categorical baseline differences will be assessed with chi-square tests and continuous differences with t-tests or Wilcoxon rank-sum tests (nonparametric) as appropriate. These tests are exploratory and will not affect the primary analysis model unless a clear need for adjustment is identified.

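### SAP 4.1 rules out hypothesis tests on baseline characteristics, but 4.2 specifies them and leaves an undefined exception through which they could change the primary model

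*SAP*

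**What the plan says.** SAP 4.1 (General Analysis Principles) states: "No formal hypothesis testing will be performed on baseline characteristics". It adds that observed differences are to be read as chance.

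SAP 4.2 (Baseline Comparisons and Participant Flow), the next subsection, states: "Categorical baseline differences will be assessed with chi-square tests and continuous differences with t-tests", or with rank-sum tests as the nonparametric alternative. On the use of the results it says two things. Where a substantial difference appears, such as "a significant age difference or stroke severity difference between groups", it says "these variables may be considered for inclusion as covariates in sensitivity analyses of outcomes". It then says of the tests themselves: "These tests are exploratory and will not affect the primary analysis model unless a clear need for adjustment is identified".

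The list of variables is open-ended: "Baseline demographic and clinical variables (age, sex, stroke type, time since stroke, baseline PHQ-9, etc".

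The primary mixed model in SAP 4.3 has group, categorical time (baseline, 1, 3 and 6 months) and their interaction as fixed effects. It names no baseline covariates. Two other places make a choice depend on observed imbalance. SAP section 3 (Other Clinical Measures) says that baseline differences in Rankin and NIHSS scores will be allowed for if that proves necessary. SAP 4.3 (Endpoint Analysis, Supportive) prefers ANCOVA to a change-score t-test when the outcome is imbalanced at baseline.

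**The concern.** The two subsections give opposite instructions on the same tests. SAP 4.2 is also inconsistent within itself: it first confines imbalanced variables to sensitivity analyses, then leaves a route into the primary model. Nothing defines when that route opens. There is no p-value or standardised-difference threshold, no candidate list, no form for the added terms and no named decision-maker.

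Under randomisation a small baseline p-value reflects chance, and it does not show that the variable predicts the outcome. A rule or judgement built on such p-values is therefore a poor way to choose covariates. At stake is whether the primary model for PHQ-9, FSS, MMSE and Barthel Index is truly fixed in advance. SAP section 1 gives the avoidance of data-driven decisions as the reason for finalising the plan early.

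**Working it through.** The plan gives no figure on this point, so there is none to reproduce.

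**1. The texts side by side.** SAP 4.1: no formal tests on baseline characteristics. SAP 4.2: chi-square, t- or rank-sum tests on those characteristics, labelled exploratory. The label does not reconcile them, because these are hypothesis tests and their result can trigger a change of model.

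**2. How often chance would raise a flag.** Inputs: α = 0.05 two-sided (SAP 4.1) and k = 5 named variables (SAP 4.2). Independence of the tests is assumed.

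P(at least one p<0.05) = 1 − 0.95^k

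- k = 5: 1 − 0.7738 = 0.226
- k = 8: 0.337; k = 10: 0.401; k = 15: 0.537. These counts are assumptions, because the list is open-ended.

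**3. What adjustment would do to the primary contrast.** Let x be a baseline covariate entered as a main effect in the SAP 4.3 model:

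y(i,t) = a(t) + g(t)·G(i) + b·x(i) + u(i) + e(i,t)

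The primary parameter is the between-group difference in change from baseline to 6 months. For one person,

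y(i,6) − y(i,0) = [a(6) − a(0)] + [g(6) − g(0)]·G(i) + e(i,6) − e(i,0)

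so b·x(i) cancels. A simulated check used 46 per arm, four visits, and age imbalanced by 0.5 SD and prognostic. With complete data it gave −1.9965 (SE 0.9972) with no covariate, with age, and with age plus the baseline score. A further simulated dataset gave −2.1762 (SE 0.9531) with and without age. With 15% assumed missing at 6 months, estimates moved by about 0.01 to 0.10 against an SE of about 1.0.

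If x enters with a time interaction, b becomes b(t) and [b(6) − b(0)]·x(i) remains in the change. The contrast can then move with the imbalance. The SAP does not say which form an added covariate would take.

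**4. Type I error.** A null simulation used 10,000 runs, 46 per arm and five independent covariates, each correlated 0.2, 0.3 or 0.4 with the outcome. It used ordinary regression on a 6-month outcome, which is only a stand-in: it lacks the cancellation in step 3.

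| Way of choosing | r = 0.2 | r = 0.3 | r = 0.4 |
|---|---|---|---|
| Adjust only for covariates with baseline p<0.05 | 0.044 | 0.037 | 0.029 |
| Report the better of unadjusted and rule-adjusted | 0.052 | 0.054 | 0.053 |
| Free pick of none, any one, or all five | 0.095 | 0.121 | 0.154 |

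Fixed choices stay nominal: 0.049 to 0.050 with no covariates and 0.047 to 0.050 with all five. The last row of the table is an upper scenario that the SAP does not describe.

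**5. The outcome's own baseline value.** With complete data, equal variances σ² and baseline-to-6-month correlation r, the per-person variance is 2σ²(1 − r) for a change score and σ²(1 − r²) after conditioning on baseline. The ratio is (1 + r)/2. For assumed r = 0.3, 0.5 and 0.7 this is 0.65, 0.75 and 0.85, a variance reduction of 35%, 25% and 15%. Constraining baseline means to be equal in the mixed model cut the SE from 0.953 to 0.851 and from 1.022 to 0.920 in two simulated datasets (ratios 0.89 and 0.90). SAP 4.3 treats the change-score t-test and ANCOVA as equivalent when baseline means are equal. That is true of the point estimate but not of its precision.

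**The case against.** The best defence is that 4.2 makes no effect on the primary model the default and calls the tests exploratory, while 4.1 already treats differences as chance. The protocol keeps the analyst blind to group labels, and SAP section 5 requires deviations to be reported. A baseline-adjusted ANCOVA is already planned as support. As step 3 shows, ordinary main-effect adjustment hardly touches the primary parameter.

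Most of this stands, and it limits the size of the problem. It does not remove the conflict between 4.1 and 4.2 or supply the missing criterion. Blinding to labels helps only in part, because the p-value and the size of the difference remain visible between coded groups. A model change made under the exception would arguably not count as a deviation, since the plan permits it.

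Three stronger readings are tempting and should be resisted:

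- A reader might infer that the baseline tests will drive covariate choice in the primary model. The text makes that an exception, not the rule.
- A reader might take 40% to 54% as the size of the harm. Those figures need 10 to 15 tested variables where five are named, and they count chance flags, not changes of model.
- A reader might infer inflated type I error, or lost precision from omitting balanced covariates. A mechanical p<0.05 rule was conservative in the stand-in, and main-effect covariates leave the primary contrast and its SE unchanged with complete data.

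**Conclusion.** The point holds as a contradiction between SAP 4.1 and 4.2, together with an undefined, data-dependent exception for the primary model. Similar open choices remain in section 3 (Rankin and NIHSS) and in the supportive analysis of 4.3. A chance flag would arise in 22.6% of perfectly randomised trials for the five named variables, assuming independence, and more often if the open list is longer.

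The consequence is an unfixed model, including the possibility of covariate-by-time terms. It is not a demonstrated large bias or error-rate inflation. The near-invariance of the primary contrast rests on main-effect entry and on complete or modestly incomplete data. The correction should be made because it is almost free and removes a post-hoc choice across four primary outcomes.

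**What to change.** - Delete the baseline tests and the exception clause from SAP 4.2. Present baseline data descriptively, as 4.1 says.
- Confine adjustment prompted by observed imbalance to sensitivity analyses labelled as such. Bring the Rankin and NIHSS sentence in section 3 into line.
- Use each outcome's baseline value whatever imbalance is seen. In the primary mixed model, either constrain baseline means to be equal across arms, or model only the 1-, 3- and 6-month visits with baseline as a covariate and a baseline-by-time term. Simply adding the baseline score to the present model is not a solution: it is already the response at time 0, and with complete data the addition changes nothing (step 3).
- In the supportive analysis of 4.3, always use ANCOVA.
- If further covariates are wanted in the primary model, name them before unblinding and state whether they enter with time interactions.

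The cost is SAP wording and at most a few degrees of freedom. The sample size does not change.
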